#### 4.1 Inclusion criteria

For inclusion in the study, patients should fulfill the following criteria:

- 1. Written informed consent.
- 2. Age  $\geq$  18 years at time of study entry.
- 3. Eastern Cooperative Oncology Group (ECOG) performance status of 0 or 1.
- 4. Life expectancy of  $\geq$  52 weeks.
- 5. Adequate normal organ and marrow function as defined below:
  - Hemoglobin  $\geq 11.0 \text{ g/dL}$ .
  - Absolute neutrophil count (ANC) ≥ 1.5 x  $10^9$ /L (≥ 1500 per mm^3).
  - Platelet count ≥  $100 \times 10^9$ /L (≥ $100,000 \text{ per mm}^3$ ).
  - Serum bilirubin  $\leq 1.5$  x institutional upper limit of normal (ULN). This will not

apply to subjects with confirmed Gilbert's syndrome (persistent or recurrent hyperbilirubinemia that is predominantly unconjugated in the absence of hemolysis or hepatic pathology), who will be allowed only in consultation with their physician.

- AST (SGOT)/ALT (SGPT)  $\leq 2.5$  x institutional upper limit of normal
- Serum creatinine CL>40 mL/min by the Cockcroft-Gault formula (Cockcroft and Gault 1976) or by 24-hour urine collection for determination of creatinine clearance:

Males	
Creatinine CL =	Weight (kg) x (140 - Age)
(mL/min)	72 x serum creatinine (mg/dL)

- 6. Subject is willing and able to comply with the protocol for the duration of the study including undergoing treatment and scheduled visits and examinations including follow up.
- 7. Consent to MD Anderson laboratory protocol PA13-0291 and LAB02-152.
- 8. Willing to have peripheral blood mononuclear cells and bone marrow biopsies to be collected prior to receiving the first dose of durvalumab and tremelimumab, after 2-doses and 4-doses of durvalumab and tremelimumab, after 2nd treatment administration and 4th treatment administration.
- 9. Histologically or cytologically confirmed adenocarcinoma of the prostate.
- 10. Evidence of metastatic disease to the bone seen on most recent bone scan, CT scan and/or MRI.
- 11. Asymptomatic or minimally symptomatic patients (do not require narcotics for prostate cancer-related pain).
- 12. Tumor progression while on hormone therapy with castrate levels serum testosterone (≤ 1.7 nmol/L or 50 ng/dL) defined by PSA and/or radiographic criteria according to the Prostate Cancer Working Group 3 (PCWG3). Castrate levels of testosterone must be maintained by surgical or medical means throughout the conduct of the study.

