# 9.1.3 Definition of radiographic PD for soft tissue tumor deposits

• An increase in tumor burden of  $\geq$  20% relative to nadir (minimum recorded tumor burden, including the baseline  $\Sigma$ p-diam if that is the smallest on study). In addition to the

relative increase of 20%, the sum must also demonstrate an absolute increase of at least 5 mm.

- In patients classified as having PD within 12 weeks of last tremelimumab dose, confirmation of PD by a second scan ≥ 4 weeks later in the absence of rapid clinical deterioration will be required, as long as the patient does not show other signs or symptoms of disease progression as judged by the investigator.
- The appearance of one or more new lesions (measurable or non-measurable) will not be considered evidence of PD as long as all of the following criteria are met:
  - The increase in tumor burden remains <20% relative to nadir.
  - There are no signs nor symptoms of disease progression (including laboratory parameters, e.g. worsening liver function tests attributable to liver metastases) as judged by the investigator.
  - O There is no further increase in tumor burden observed in a repeat, consecutive assessment obtained  $\geq 4$  weeks later.
  - o For non-measurable tumor lesions an increase in overall disease burden comparable in magnitude to the increase that would be required to declare PD for measurable disease (i.e. ≥20%) will be considered evidence of PD.
  - o If repeat scans confirm PD, then progression should be declared using the date of the initial scan.

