## 9.4 Definition of progression of disease

For the purposes of this study, progression of disease (PD) is a composite endpoint, consisting of clinical deterioration and/or radiographic progression as defined below. Subjects with PSA progression alone will not be considered to have PD.

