# 11.1.2 Efficacy analysis set

To be evaluable for the secondary objectives, a patient needs to receive 2 doses of drug, have immune markers measured, and have at least one follow-up for clinical outcome measures. Patients who do not meet this level of evaluability will be described separately to establish any

trends in patient evaluability and comparability of compliant patients with the intended patient population based on available information.

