# 11.2.2 Efficacy analyses

Efficacy of this combination will be measured by PSA progression-free survival (PFS), radiographic PFS, and maximal decline of PSA from baseline. PSA PFS, radiographic PFS, and time to maximal PSA decline will start at the first day of treatment and will be summarized by Kaplan-Meier. The numeric PSA value at maximal decline will be summarized by a boxplot and as a scatter plot of maximal decline by baseline PSA.

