# 11.2.3 Biomarker endpoint analyses

For continuous data, summary statistics including n, mean, standard deviation, median, minimum and maximum or IQR will be computed. Prostatic T cell infiltration pre-and-post biopsy will be described and graphed over time. Differences in either time point compared to baseline will be compared with a t-test or non-parametric alternative. Cox models will be implemented to explore the relationship of treatment combination, prostatic T cell infiltration, and progression-free survival.

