# 11.3 Determination of sample size

The selection of 20 evaluable patients was intended as a pilot sample size with sufficient numbers to establish safety in this population as shown in Table 5 above while providing sufficient numbers for the secondary endpoints. This will allow investigation of a few marker endpoints and establish safety and feasibility of measuring the markers of interest while being able to accrue within 6 months. No formal hypotheses are planned. These patients will form the basis of designing a hypothesis-driven study in the future. However, we can make a statement about what might be detected in secondary endpoints at this sample size. The association between CD3 change and PSA PFS will be explored with a Cox model with CD3 as a continuous measure. Assuming that

75% (80%) of patients will progress by the end of the study, 20 patients will have 80% power to detect a regression coefficient of 0.72 (0.70) at a 2-sided 5% significance level, assuming the change in CD3 has a standard deviation of 1. The regression coefficient of 0.72 (0.70) is equivalent to a hazard ratio of 2.1 (2.0) or a doubling of risk per unit increase in CD3 (Calculations performed in NCSS-PASS 2005). This would hold true for both biomarker and any model of PSA PFS or Radiological/Clinical PFS.

Even if fewer than 20 patients have information available, this is the first look at these measures. Therefore, the descriptive information gathered on biological markers and outcomes, as well as the feasibility of collecting such information in future trials will be valuable.

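### CD3 change is sampled after 2 or 4 doses but related to PFS counted from day 1, with no defining sample and no landmark, so some PFS events can precede the CD3 value used to explain them

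*Combined protocol and SAP*

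**What the plan says.** All references are to the combined protocol and SAP.

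- **Time origin (11.2.2):** "PSA PFS, radiographic PFS, and time to maximal PSA decline will start at the first day of treatment".
- **Sampling (4.1, item 8):** patients must accept blood sampling and "bone marrow biopsies to be collected prior to receiving the first dose of durvalumab and tremelimumab, after 2-doses and 4-doses". Table 1 places dose 2 at week 4 and dose 4 at week 12. It has no biopsy row, so no sampling day is fixed.
- **Biomarker analysis (11.2.3):** "Differences in either time point compared to baseline will be compared with a t-test or non-parametric alternative", and then "Cox models will be implemented to explore the relationship of treatment combination, prostatic T cell infiltration, and progression-free survival".
- **Sample size (11.3):** "The association between CD3 change and PSA PFS will be explored with a Cox model with CD3 as a continuous measure". The section claims 80% power for a coefficient of 0.72 (0.70) if 75% (80%) of 20 patients progress, and extends the claim to radiological/clinical PFS.
- **Evaluability (11.1.2):** "a patient needs to receive 2 doses of drug, have immune markers measured, and have at least one follow-up for clinical outcome measures".
- **Progression (9.4):** "Subjects with PSA progression alone will not be considered to have PD". Clinical deterioration (9.4.1) does count and is not tied to a visit.
- **Dating of scan progression (9.1.3, and likewise 9.2.1):** "If repeat scans confirm PD, then progression should be declared using the date of the initial scan".

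**The concern.** A Cox model with a fixed covariate treats that covariate as known from the time origin. Here the origin is day 1, but the covariate does not exist until after dose 2 or dose 4. A patient whose event is dated before the sample enters the risk sets with a value measured after the event. If progression itself changes CD3 in tissue, the fitted association partly runs backwards, from progression to CD3.

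The plan leaves this open in three places: it does not say which sample defines the change, how events before the sample are handled, or whether a patient must be event-free when sampled.

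Section 3.1 presents the link between immune changes and efficacy as what the pilot explores, and 11.3 intends these patients to inform a later hypothesis-driven study. The stake is a possibly misleading lead for that study. No decision within this trial depends on it.

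**Working it through.** **1. The plan's own figure.** Inputs from 11.3: N = 20, 75% (80%) progressing, SD of CD3 change = 1, two-sided 5%, 80% power. Events D = 20 × 0.75 = 15 (20 × 0.80 = 16). Detectable coefficient B = (1.960 + 0.842)/(SD × √D):
- D = 15: 2.802/√15 = 0.723; the stated 0.72 gives HR exp(0.72) = 2.05.
- D = 16: 2.802/√16 = 0.700; exp(0.70) = 2.01.

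The stated figures reproduce. They count every event from day 1.

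**2. Which events can precede the sample.**

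| Event | After-2-dose sample (dose at week 4) | After-4-dose sample (dose at week 12) |
|---|---|---|
| PSA, every cycle (Table 1) | week 4 | weeks 4, 8, 12 |
| Scan, first on treatment at week 8, window ±7 days | only if done early (week 7) and the sample is taken late | week 8 |
| Clinical deterioration, unscheduled (9.4.1) | possible | possible |

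Such patients can still be sampled. PSA progression alone is not PD, so it does not by itself end treatment. A week-8 scan progression generally needs confirmation at least 4 weeks later and is then dated back. Stopping for progression requires confirmed PD plus the investigator's judgement (4.3, item 7), and 6.2.2 allows treatment past progression. PSA progression is not defined for PSA PFS, so whether a week-4 rise counts is open.

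**3. How many events.** The documents give no PFS distribution and no follow-up length. Assume a constant hazard with proportion p progressed by week T. Expected events by week t in 20 patients = 20 × [1 − (1 − p)^(t/T)]. For example, p = 0.75, T = 48, t = 12: 20 × (1 − 0.25^0.25) = 5.9.

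| p, T | week 4 | week 8 | week 12 | week 16 |
|---|---|---|---|---|
| 75%, 48 | 2.2 | 4.1 | 5.9 | 7.4 |
| 75%, 104 | 1.0 | 2.0 | 3.0 | 3.8 |
| 80%, 48 | 2.5 | 4.7 | 6.6 | 8.3 |
| 80%, 104 | 1.2 | 2.3 | 3.4 | 4.4 |

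Read at the scheduled visits, this gives 1.0-2.5 PSA events by week 4, 3.0-6.6 by week 12, and 2.0-4.7 scan events at week 8. Only patients actually sampled after their event matter, and that number is unknown.

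**4. What it could do to the test.** Null simulation: N = 20, CD3 unrelated to later risk, CD3 shifted by an assumed amount when the event precedes the sample, PSA 4-weekly, scans 8-weekly to week 48 then 12-weekly, Wald test at nominal 5%, Breslow ties, 8,000 trials per cell. The ranges cover both values of p and both values of T.

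| Assumption | After 2, PSA | After 4, PSA | After 4, scans |
|---|---|---|---|
| 1 SD shift, all sampled | 6-8% | 12-21% | 7-11% |
| 1 SD shift, half of early progressors unsampled | 5% | 7-11% | 5-6% |
| 0.5 SD shift, all sampled | 5% | 6-8% | 4-5% |

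With no shift, or with a landmark, rejection is 2-5%. With Efron ties (4,000 trials), the first row becomes 7-12%, 12-25% and 9-19%, no shift gives 5-6%, and the landmark 4-6%. With a 0.5 SD shift and half of early progressors unsampled (75% progressing, 1,500 trials), rejection is 4-5% (Breslow) or 5-8% (Efron), against 3-6% with no shift.

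A cruder run used continuous event times, counted every event before week 8 or week 16 as preceding the sample, and set T to 48 or 96. A 1 SD shift gave 10-16% (week 8) and 17-30% (week 16).

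The after-2-dose column counts only the week-4 PSA visit as preceding the sample. It leaves out early clinical deterioration and an early scan.

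**5. Price of a landmark.** Take the plan's 15 events and subtract those before the landmark. At week 8 with T = 48: 15 − 4.1 = 10.9 and 2.802/√10.9 = 0.85, HR 2.34, power at 0.72 of 66%. Over landmarks at weeks 4-8 and T = 48-104, the detectable HR is 2.12-2.34. Over weeks 12-16 it is 2.24-2.76, with power at 0.72 of 70% down to 51%. These values rest on the assumed hazards.

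**The case against.** The strongest reply has four parts.

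- **The 2-dose sample is the natural reading.** Evaluability (4.4, 11.1.2) rests on 2 doses and never requires a 4-dose sample. With the after-2-dose sample the simulated inflation is small. This largely stands, and it is why that sample is the right one to name. But the evaluability rule does not define the Cox covariate, and 11.2.3 uses both time points.
- **The bias rests on an assumed shift.** This stands. Without a CD3 change after progression there is no bias of this kind, and full sampling of early progressors is optimistic for the after-4-dose sample. The rates also move with the tie method, so they are illustrations, not estimates.
- **Sampling days may be set elsewhere.** Section 8.2.1 takes correlative samples from other institutional biospecimen protocols. That may fix the dates, but it would not supply a landmark in this analysis.
- **The analysis is exploratory.** Section 11.3 plans no formal hypotheses and accepts fewer than 20 patients with data. This limits the consequence but does not remove the timing problem.

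A reader might infer that the power statement is wrong, or that the planned Cox model will have a false-positive rate of 20% or more. The documents support neither: the power reproduces for events from day 1, and they give no post-progression CD3 shift and no count of patients sampled after their event.

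**Conclusion.** The concern holds as a gap in timing and specification. As written, the Cox models allow PFS events to precede the CD3 value used to explain them. Exposure is modest for the after-2-dose sample: mainly a week-4 PSA event, but also early clinical deterioration or a scan done early in its window. It is larger for the after-4-dose sample: PSA events at weeks 4-12, and a week-8 scan progression confirmed later and dated back.

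Whether this biases the association depends on progression altering CD3, which the documents do not address. A false-positive rate of roughly 10-20% or more arises only under a 1 SD shift with the after-4-dose sample and PSA PFS, and varies with follow-up length, tie handling and how many early progressors are sampled. For a small shift, or where early progressors go unsampled, the rate is close to nominal. The event counts assume a constant hazard and 75-80% progressed by week 48 to week 104. This is a cheap improvement to an exploratory analysis.

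**What to change.** Amend 11.2.3 and 11.3 as follows:

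1. Name the after-2-dose sample as defining CD3 change in the main exploratory Cox model. It matches the 2-dose evaluability rule.
2. Start PFS at that sample among patients still event-free, or enter CD3 as a time-dependent covariate from the sample date.
3. Treat the after-4-dose sample in the same way, as a secondary analysis.
4. Report the number of PFS events before each sample.
5. Beside the power statement, note that it counts all events from day 1, and that fewer events, hence a somewhat larger detectable HR, will apply after the landmark. Do not fix a number there, since it would come from assumed hazards.

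The cost is SAP wording only: no new patients, visits or samples. The downside is that early progressors leave the landmark analysis and some power is lost.

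### The 80% power stated for the CD3 Cox model is an unlabelled large-sample value; with 20 patients and a normally distributed marker, simulated power is about 62–69%

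*Combined protocol and SAP*

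**What the plan says.** Section 11.3 presents 20 evaluable patients as a pilot size and states "No formal hypotheses are planned". It then introduces a power statement: "However, we can make a statement about what might be detected in secondary endpoints at this sample size". The model is described as follows: "The association between CD3 change and PSA PFS will be explored with a Cox model with CD3 as a continuous measure". On the premise that "75% (80%) of patients will progress by the end of the study", the section says that "20 patients will have 80% power to detect a regression coefficient of 0.72 (0.70) at a 2-sided 5% significance level". A further condition sets the scale of the marker: "assuming the change in CD3 has a standard deviation of 1". The section translates the coefficients into hazard ratios of 2.1 (2.0) and names the software, NCSS-PASS 2005.

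It names no formula and no test. It gives no distribution for the CD3 change and no censoring pattern, and it does not call the figure approximate. It then widens the claim: "This would hold true for both biomarker and any model of PSA PFS or Radiological/Clinical PFS".

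**The concern.** For a continuous covariate, the standard calculation depends only on the number of events, the covariate SD and the coefficient. It treats the covariate variance among patients still at risk as constant over follow-up. With 20 patients, 15 or 16 of whom fail, and a strong effect, that is doubtful. Patients with high-risk marker values tend to fail early, so the later risk sets are small and hold little marker spread. The data then carry less information than the event count implies.

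Section 11.3 says these patients will be the basis for designing a hypothesis-driven study. A reader who takes 80% at face value expects a doubling of risk per SD to be missed one time in five. If the true figure is nearer one in three, a null CD3 result from this trial could be over-read when that study is planned.

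**Working it through.** **Inputs, all from Section 11.3.** n = 20; event proportion 75% (80%), so 20 × 0.75 = 15 and 20 × 0.80 = 16 events; coefficient β = 0.72 (0.70); SD = 1; two-sided 5%; one continuous covariate in a Cox model.

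**Reproducing the plan's figure.** Power = Φ(√D × SD × β − 1.96), where D is the number of events.

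- D = 15, β = 0.72: Φ(3.873 × 0.72 − 1.96) = Φ(0.829) = 0.796.
- D = 16, β = 0.70: Φ(4 × 0.70 − 1.96) = Φ(0.84) = 0.800.
- Hazard ratios: exp(0.72) = 2.05 and exp(0.70) = 2.01, matching the stated 2.1 and 2.0.

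So the plan's figure is the large-sample formula value, correctly computed.

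**Simulation at n = 20.** Assumptions added here: hazard proportional to exp(βX), exponential event times, X normal with SD 1. There were 20,000 runs per setting, so the Monte Carlo standard error is about √(0.65 × 0.35 / 20,000) = 0.003. Each cell gives power for the Wald / likelihood ratio / score test.

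| Setting | Longest times censored | Independent exponential censoring | Randomly chosen patients censored |
|---|---|---|---|
| Normal, 15 events, β = 0.72 | 0.670 / 0.691 / 0.684 | 0.626 / 0.654 / 0.647 | 0.616 / 0.647 / 0.637 |
| Normal, 16 events, β = 0.70 | 0.663 / 0.684 / 0.676 | 0.631 / 0.655 / 0.648 | 0.629 / 0.657 / 0.650 |
| Sample SD exactly 1, 15 events, β = 0.72 | 0.695 / 0.718 / 0.709 | 0.644 / 0.672 / 0.664 | 0.639 / 0.669 / 0.661 |
| Sample SD exactly 1, 16 events, β = 0.70 | 0.693 / 0.715 / 0.706 | 0.648 / 0.676 / 0.668 | 0.641 / 0.670 / 0.664 |

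A separately programmed simulation (6,000 runs per setting, also covering a fixed administrative cut-off and uniform censoring) gave 0.63–0.70 for the normal marker.

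**Is the gap a coding fault or a conservative test?** Neither.

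- With n = 400, 300 events and a coefficient of 0.162, the formula gives Φ(√300 × 0.162 − 1.96) = Φ(0.846) = 0.80. The simulation gives 0.791.
- At n = 20 the null rejection rate is 0.050–0.061 for the normal and fixed-SD markers, so the tests are not conservative.
- With SD 1 the formula takes the information as equal to the event count, 15. The simulated mean information at the fitted coefficient was 9.7 (longest times censored) or 7.9 (randomly chosen patients censored).

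**Other marker shapes (SD 1, both coefficients).**

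| Shape | Power |
|---|---|
| Uniform | 0.64–0.72 |
| t with 5 degrees of freedom | 0.58–0.65 |
| Right-skewed (log-normal, sigma 0.5) | 0.58–0.70 |
| Mirror image of that | 0.46–0.63 |
| Two-group or clustered, exactly 6 of 20 high, longest times censored | 0.77–0.85 |
| Same, random censoring | 0.67–0.79 |
| Clustered, random group membership, longest times censored | 0.73–0.80 |
| Same, random censoring | 0.64–0.75 |

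The top value, 0.85, comes from a strict two-point marker and the score test. The continuous clustered version reaches at most 0.835. For these shapes the null rejection rate runs up to 0.069, highest for the score test.

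**Coefficient needed for 80% power.** Normal marker: 0.85–0.94 with 15 events and 0.83–0.91 with 16, a hazard ratio of about 2.3–2.5 per SD. With the sample SD fixed at 1: 0.81–0.89 and 0.79–0.86, a hazard ratio of about 2.2–2.4.

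**The case against.** The best defence has three parts.

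**There is no arithmetic error, and the formula is conventional.** This is true. The section gives enough to reproduce 80%. But convention supports using the formula; it does not support stating its result without qualification at 15 or 16 events, where it is more than 10 points too high for a normal marker.

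**The 62–69% rests on assumptions the plan does not make.** This is also true. The plan fixes only the SD. Normality, exponential times and the censoring pattern are added here, and over all shapes tried power ran from 0.46 to 0.85. So 62–69% is not the power of this trial; it is the power in one reasonable reference case for a marker entered as continuous. What survives is narrower: most shapes tried fall short of 80%, clustered ones can reach it, and the section gives no hint that the figure is conditional.

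**Little depends on it.** The primary objective is safety, the association is only to be explored, and Section 11.3 accepts that fewer than 20 patients may have data. This stands, and it limits the weight of the point. It does not make the stated figure right.

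The extension sentence can be read as applying under the same assumptions, but it does not say so. It gives no SD for another marker and no event fraction for Radiological/Clinical PFS. Section 11.2.3 plans Cox models that also bring in treatment combination, so the reference to any model reaches beyond a single-covariate calculation.

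**Conclusion.** The concern holds. The 80% is a correctly computed large-sample value presented as the power of a 20-patient Cox analysis. With a normal CD3 change of SD 1 and exponential times, power is about 62–69% for both coefficients, or about 64–72% if the sample SD is exactly 1. A doubling of risk per SD would then be missed about one time in three. The shortfall is a small-sample effect and depends on marker shape and censoring; it can disappear for a clustered marker. The practical consequence is modest, since no design decision rests on the number, but the text should be corrected because nothing else in the plan quantifies what the secondary endpoints can detect.

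**What to change.** In Section 11.3, label the 80% as a large-sample approximation and add the simulated value with its conditions, for example:

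> By simulation with a normally distributed CD3 change (SD 1) and exponential times, 20 patients with 15 (16) events give about 62–69% power for a coefficient of 0.72 (0.70), over Wald, likelihood ratio and score tests and several censoring patterns. Power of 80% needs a coefficient of about 0.85–0.94 (0.83–0.91), a hazard ratio of about 2.3–2.5 per SD. Power depends on the marker's distribution and the censoring pattern and can be higher or lower for other shapes.

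If the team expects a particular CD3 distribution or follow-up pattern, it should simulate that case and report it instead. Restrict the extension sentence to single-covariate models, with effects per SD of the marker, the same event fraction and complete data on 20 patients.

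The cost is a few lines of protocol text and a short simulation. Enrolment, stopping rules and analyses do not change. The only downside is a less favourable stated figure.
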